4.0 SELECTION AND ENROLLMENT OF PARTICIPANTS

4.1 Inclusion Criteria for Step 1

4.1.1 New or recurrent pulmonary TB with sputum positive for acid-fast bacilli on direct microscopy of at least grade 1+ (International Union Against Tuberculosis and Lung Disease [IUATLD] scale) at the study laboratory on at least one pre-treatment sputum sample within 14 days prior to entry.

4.1.2 Age ≥ 18 and ≤ 65 years at study entry.

4.1.3 Infected with an *M. tuberculosis* strain for which Hain GenoType MTBDRplus genotype, performed at the study laboratory within 14 days prior to study entry, reveals one of the following results for INH susceptibility testing:

- *inhA* promoter or functional mutation only (Group 1 participants, eligible for Steps 1 and 2)
- No mutations in the *inhA* or *katG* genes (Group 2 participants, eligible for Step 1 and, during Stage 2 of the study, also eligible for Step 2)
- *katG* mutation with or without an *inhA* mutation (Group 3 participants, **eligible for Step 1 and, during Stage 2 of the study, also eligible for Step 2**)

4.1.4 Ability and willingness of the participant or legal guardian/representative to provide informed consent.

4.2 Exclusion Criteria for Step 1

There are no exclusion criteria for Step 1.

4.3 Inclusion Criteria for Step 2

4.3.1 Entry into Step 1.

4.3.2 During Stage 1 of the protocol: *inhA* promoter or functional mutation only (Group 1).

During Stage 2 of the protocol: *inhA* promoter or functional mutation only (Group 1) OR mutations in neither *inhA* nor *katG* genes (Group 2) **or mutation in the *katG* gene, with or without mutations in *inhA* promoter or functional genes (Group 3).**

4.3.3 Body weight: 40 kg to 90 kg, inclusive.

4.3.4 Laboratory values obtained within 30 days prior to entry:

- Absolute neutrophil count (ANC) ≥ 750 cells/mm³
- Hemoglobin ≥ 7.4 g/dL
- Platelet count $\geq 50,000$ /mm³
- Aspartate aminotransferase (AST) and alanine aminotransferase (ALT) ≤ 3 X upper limit of normal (ULN)
- Total bilirubin ≤ 2.5 X ULN

4.3.5 HIV infection status must be documented as either absent or present, as defined below:

Absence of HIV-1 infection, as documented by any licensed rapid HIV test or HIV enzyme or chemiluminescence immunoassay (E/CIA) test kit, within 30 days prior to Step 2 entry.

OR

HIV-1 infection, documented by any licensed rapid HIV test or HIV enzyme or chemiluminescence immunoassay (E/CIA) test kit at any time prior to Step 2 entry and confirmed by a licensed Western blot or a second antibody test by a method other than the initial rapid HIV and/or E/CIA, or by HIV-1 antigen or plasma HIV-1 RNA viral load.

NOTE: The term “licensed” refers to a US FDA-approved kit, which is recommended. For sites that are unable to obtain an FDA-approved kit, a kit that has been certified or licensed by an oversight body within the country and validated internally is acceptable.

WHO and Centers for Disease Control and Prevention (CDC) guidelines mandate that confirmation of the initial test result must use a test that is different from the one used for the initial assessment. A reactive initial rapid test should be confirmed by either another type of rapid assay or an E/CIA that is based on a different antigen preparation and/or different test principle (e.g., indirect versus competitive), or a Western blot or a plasma HIV-1 RNA viral load.

- 4.3.6 For HIV-positive candidates only: CD4+ cell count of ≥ 50 cells/mm³, performed within 7 days prior to entry at a DAIDS-approved laboratory.
- 4.3.7 For females of reproductive potential, negative serum or urine pregnancy test within 7 days prior to entry. Female participants who are participating in sexual activity that could lead to pregnancy must agree to use one reliable non-hormonal method of contraception (condoms or an IUD), or another method (diaphragm or cervical cap) if it is approved by the national regulatory authority and used according to package insert, while receiving study medications.

NOTE: Female participants who are not of reproductive potential or whose male partner/s has/have undergone successful vasectomy with documented azoospermia or has/have documented azoospermia for any other reason, are eligible without requiring the use of contraceptives. Participant-reported history is acceptable documentation of menopause (i.e., at least 1 year amenorrheic), hysterectomy, or bilateral oophorectomy or bilateral tubal ligation; these participants are all considered not of reproductive potential.

- 4.3.8 Willingness to be hospitalized for a minimum of 9 consecutive days.
- 4.3.9 Ability to produce an overnight sputum sample of sufficient quality and quantity. As a guideline, this should be 10 mL or more during a 16-hour collection period.

NOTE: If a participant’s failure to produce sufficient sputum appears to be due to poor technique rather than low volume of sputum production, this evaluation may be repeated.

4.4 Exclusion Criteria for Step 2

4.4.1 Current treatment with INH or receipt of INH during the 7 days prior to Step 2 entry.

NOTE: Participants who have been started on INH-containing anti-TB treatment and have received this treatment for less than or equal to 2 weeks, but for whom TB drugs have been discontinued because of resistance to INH (with or without resistance to RIF), can participate in the study, but may need to be hospitalized, at the discretion of the investigator, while these drugs wash out; the minimum washout period for these drugs is 7 days.

4.4.2 **Receipt of more than 7 cumulative days of second-line anti-TB drugs (including all drugs with anti-TB activity, except INH, RIF, ethambutol, pyrazinamide, and streptomycin) and/or antibiotics intended for bacterial treatment that may have anti-TB activity, including amoxicillin/clavulanate (Augmentin), linezolid, metronidazole, or drugs from the quinolone class, within the 14 days prior to Step 1 screening sputum collection. The minimum washout period for these drugs is 7 days prior to Step 2 pre-entry sputum collection.**

4.4.3 Known exposure to a person diagnosed with XDR-TB or known personal diagnosis of XDR-TB in the past.

4.4.4 Breastfeeding.

4.4.5 Known allergy/sensitivity to INH.

4.4.6 Karnofsky score <60 or poor general condition where any delay in full TB treatment cannot be tolerated in the opinion of the investigator (at screening).

4.4.7 Any of the following co-morbidities, complications, or underlying medical conditions:

- Known current neurological TB (e.g., TB of the spine, TB meningitis)
- Peripheral neuropathy \geq Grade 2, according to the December 2004 (Clarification, August 2009) Division of AIDS (DAIDS) Toxicity Table, within 14 days prior to entry
- Current or history of epilepsy, defined as seizure disorder requiring current treatment with an antiepileptic medicine or history of any seizures within the prior year

4.4.8 Any condition as determined by physical examination, medical history, laboratory data, or chest x-ray which, in the opinion of the investigator, would interfere with participation in the study.

4.5 Study Enrollment Procedures

4.5.1 Prior to implementation of this protocol, and any subsequent full version amendments, each site must have the protocol and the protocol consent form(s) approved, as appropriate, by their local institutional review board (IRB)/ethics committee (EC) and any other applicable regulatory entity (RE). Upon receiving final approval, sites will submit all required protocol registration documents to the DAIDS Protocol Registration Office (DAIDS PRO) at the Regulatory Support Center (RSC). The DAIDS PRO will review the submitted protocol registration packet to ensure that all of the required documents have been received. Site-specific informed consent forms (ICFs) will be reviewed and approved by the DAIDS PRO and sites will receive an Initial Registration Notification from the DAIDS PRO that indicates successful completion of the protocol registration process. A copy of the Initial Registration Notification should be retained in the site's regulatory files.

Upon receiving final IRB/EC and any other applicable RE approvals for an amendment, sites should implement the amendment immediately. Sites are required to submit an amendment registration packet to the DAIDS PRO at the RSC. The DAIDS PRO will review the submitted protocol registration packet to ensure that all the required documents have been received. Site-specific ICFs will not be reviewed and approved by the DAIDS PRO, and sites will receive an Amendment Registration Notification when the DAIDS PRO receives a complete registration packet. A copy of the Amendment Registration Notification should be retained in the site's regulatory files.

For additional information on the protocol registration process and specific documents required for initial and amendment registrations, refer to the current version of the DAIDS Protocol Registration Manual.

Protocol activation is required prior to enrolling participants into the study. The Network Coordinating Center will provide notification of activation.

Once a candidate for study entry has been identified, details will be carefully discussed with the participant. The participant will be asked to read and sign the approved protocol consent form.

For participants from whom a signed informed consent has been obtained, an ACTG Screening Checklist must be entered through the Data Management Center (DMC) Subject Enrollment System.

4.5.2 Registration/Randomization

For participants from whom informed consent has been obtained, but who are deemed ineligible or who do not enroll into the initial protocol step, an ACTG Screening Failure Results form must be completed and keyed into the database.

Patients who are eligible for participation in the study based on screening results will be registered to the protocol at the time of enrollment.

During Stage 1, Group 1 participants who meet Step 2 entry criteria will be randomized 1:1:1 to one of three doses of INH (5, 10, or 15 mg/kg). Group 1 participants who do not meet Step 2 entry criteria, as well as Group 2 and 3 participants will be enrolled in Step 1, but will not receive study drug. They will be discontinued from the study after their Step 1, Day 0 visit and referred for standard local TB treatment.

During Stage 2, Group 1 participants who meet Step 2 entry criteria will be randomized as during Stage 1. Group 2 participants who meet Step 2 entry criteria will be registered and assigned to receive 5 mg/kg study drug daily.

Group 3 participants who meet Step 2 entry criteria will be randomized 1:1 to receive 15 mg/kg or 20 mg/kg study drug daily. Group 1, 2, or 3 participants who do not meet Step 2 entry criteria will be enrolled in Step 1, but will not receive study drug. They will be discontinued from the study after their Step 1 Day 0 visit and referred for standard local TB treatment.

During Stage 2, enrollment of Group 2 participants will proceed so that, on average, for every two Group 1 participants enrolled in Step 2 per month, one Group 2 participant will be enrolled. The enrollment for Group 2 will be controlled by setting a recruitment limit, and it will be manually adjusted by the data manager and statisticians routinely (e.g., every month or twice per month).

4.6 Coenrollment Guidelines

Sites are encouraged to coenroll participants in A5243, “Plan for Obtaining Human Biological Samples at Non-US Clinical Research Sites for Currently Unspecified Genetic Analyses.” Coenrollment in A5243 does not require permission from the A5312 protocol chairs. For specific questions and approval for coenrollment in other studies, sites must contact the protocol chairs via e-mail as described in the [Study Management section](#).

5.0 STUDY TREATMENT

INH is approved for use by the US FDA for the treatment of DS-TB. The recommended dose of INH is 5 mg/kg (up to 300 mg daily) once daily for active TB. For the treatment of latent TB infection, the recommended dose is 10-15 mg/kg (up to 900 mg) twice- or thrice-weekly. In this study, INH will be given at 5 mg/kg daily to participants with DS-TB and at 5, 10, or 15 mg/kg once daily, for a total of seven daily doses, to participants infected with *M. tuberculosis* that has an *inhA* resistance mutation **or at a dose of 15 or 20 mg/kg to participants infected with M. tuberculosis that has a katG mutation.** The rationale for the higher doses is to try to overcome INH resistance by increasing the dose. In addition, participants will receive vitamin B6 ≥ 25 mg daily.

5.1 Regimens, Administration, and Duration

Stage 1Step 1:

Group 1: Participants in Group 1 who do not meet Step 2 entry criteria but are enrolled for determination of MIC only will not receive study drug.

Groups 2 and 3: In Stage 1, participants infected with *M. tuberculosis* with neither *katG* nor *inhA* mutations (Group 2) and those infected with *M. tuberculosis* with a *katG* mutation with or without an *inhA* mutation (Group 3) will not receive study drugs.

Step 2:

Group 1 (n=15): Participants infected with *M. tuberculosis* with an isolated *inhA* mutation will be randomized 1:1:1 to receive the following treatments for 7 days:

5 mg cohort	INH 5 mg/kg by mouth once daily on Days 1-7 plus vitamin B6 \geq 25 mg daily
10 mg cohort	INH 10 mg/kg by mouth once daily on Days 1-7 plus vitamin B6 \geq 25 mg daily
15 mg cohort	INH 15 mg/kg by mouth once daily on Days 1-7 plus vitamin B6 \geq 25 mg daily

Stage 2Step 1:

Participants who do not meet Step 2 entry criteria but are enrolled only for determination of MIC will not receive study drug.

Step 2:

Group 1 (n=33): Participants infected with *M. tuberculosis* with an isolated *inhA* mutation will be randomized 1:1:1 to receive the following treatments for 7 days:

5 mg cohort	INH 5 mg/kg by mouth once daily on Days 1-7 plus vitamin B6 \geq 25 mg daily
10 mg cohort	INH 10 mg/kg by mouth once daily on Days 1-7 plus vitamin B6 \geq 25 mg daily
15 mg cohort	INH 15 mg/kg by mouth once daily on Days 1-7 plus vitamin B6 \geq 25 mg daily

Group 2 (n=16): Participants infected with *M. tuberculosis* with neither *katG* nor *inhA* mutations who meet the Step 2 entry criteria will receive the following treatment for 7 days:

Control	INH 5 mg/kg by mouth once daily on Days 1-7 plus vitamin B6 ≥25 mg daily
---------	--

Group 3 (n=20): Participants infected with *M. tuberculosis* with a *katG* mutation, with or without an *inhA* mutation, who meet the Step 2 entry criteria will receive the following treatment for 7 days:

katG 15 mg cohort	INH 15 mg/kg by mouth once daily on Days 1-7 plus vitamin B6 ≥25 mg daily
katG 20 mg cohort	INH 20 mg/kg by mouth once daily on Days 1-7 plus vitamin B6 ≥25 mg daily

INH is available in 100 mg tablets. INH will be administered orally daily in the morning on an empty stomach. Doses of INH will be given according to the weight bands outlined below:

Dose cohort	Weight	Dose
5 mg/kg	≥40 kg and ≤70 kg	300 mg
5 mg/kg	>70 kg and ≤90 kg	400 mg
10 mg/kg	≥40 kg and ≤55 kg	500 mg
10 mg/kg	>55 kg and ≤65 kg	600 mg
10 mg/kg	>65 kg and ≤75 kg	700 mg
10 mg/kg	>75 kg and ≤85 kg	800 mg
10 mg/kg	>85 kg and ≤90 kg	900 mg
15 mg/kg	≥40 kg and ≤43 kg	600 mg
15 mg/kg	>43 kg and ≤50 kg	700 mg
15 mg/kg	>50 kg and ≤57 kg	800 mg
15 mg/kg	>57 kg and ≤63 kg	900 mg
15 mg/kg	>63 kg and ≤70 kg	1000 mg
15 mg/kg	>70 kg and ≤76 kg	1100 mg
15 mg/kg	>76 kg and ≤83 kg	1200 mg
15 mg/kg	>83 kg and ≤90 kg	1300 mg
20 mg/kg	≥40 kg and ≤43 kg	800 mg
20 mg/kg	>43 kg and ≤48 kg	900 mg
20 mg/kg	>48 kg and ≤53 kg	1000 mg
20 mg/kg	>53 kg and ≤58 kg	1100 mg
20 mg/kg	>58 kg and ≤63 kg	1200 mg
20 mg/kg	>63 kg and ≤68 kg	1300 mg

Dose cohort	Weight	Dose
20 mg/kg	>68 kg and ≤73 kg	1400 mg
20 mg/kg	>73 kg and ≤78 kg	1500 mg
20 mg/kg	>78 kg and ≤83 kg	1600 mg
20 mg/kg	>83 kg and ≤88 kg	1700 mg
20 mg/kg	>88 kg and ≤93 kg	1800 mg

Participants will receive INH at the assigned dose for 7 days and then will be referred to the local/national TB program for TB treatment by Day 10 (or earlier if study treatment is prematurely discontinued). Results of study-related DST will be provided to the treatment program for their use, as appropriate.

5.2 Study Product Formulation and Preparation

INH tablets locally procured by the sites must be stored in accordance with the manufacturer's instructions and be the same strength and formulation for the duration of the study.

5.3 Pharmacy: Product Supply, Distribution, and Accountability

5.3.1 Study Product Acquisition/Distribution

INH and vitamin B6 will be obtained locally for use by study participants.

INH will be obtained from a source matching at least one of the following qualifications:

- Approved by the U.S. FDA
- Approved by a country listed under the Federal Food, Drug, and Cosmetic Act Chapter VIII, Section 802(b) (1) (A) (These countries are Australia, Canada, Israel, Japan, New Zealand, Switzerland, South Africa, or the countries of the European Union or country in the European Economic Area)
- Approved by and listed under the WHO Prequalification Programme (<http://extranet.who.int/prequal/>)

Each CRS conducting A5312 must obtain the approval for use of locally procured INH tablets from the protocol team prior to administration to A5312 participants and keep a detailed log of the manufacturer information (name and location), strength and dosage form, each lot number, expiration date, and start and stop dates for usage of that lot number. This is in addition to the accountability records required in [section 5.3.2](#).

The source of vitamin B6 must also meet the requirements of this policy.

5.3.2 Study Product Accountability

The Clinical Research Site Pharmacist of Record is required to maintain records of all study products received and dispensed to study participants, and final disposition of all study products.

5.4 Concomitant Medications

Below are lists of selected concomitant medications. These lists are only current as of the date of this protocol. Whenever a concomitant medication or study agent is initiated or a dose changed, investigators must review the concomitant medications' and study agents' most recent package inserts, Investigator's Brochures, or updated information from DAIDS to obtain the most current information on drug interactions, contraindications, and precautions.

Additional drug information may be found on the ACTG Drug Interactions Database, located at: http://tprc.pharm.buffalo.edu/home/di_search/.

5.4.1 Required Medications

TB-Drug-Induced Peripheral Neuropathy Prophylaxis

Vitamin B6 (pyridoxine) once daily while participant is receiving INH; vitamin B6 will be required and provided by the site. A dose of 25 mg is recommended but may be higher based on the current local, national, or international dosing guidelines.

5.4.2 Prohibited Medications

Use of other anti-TB medications is prohibited from screening until after the final dose of study medications. Antacids must not be given together with the study drug.

5.4.3 Precautionary Medications

For a list of precautionary medications, refer to the ACTG Drug Interactions Database (see link above).

5.5 Adherence Assessment

Study doses of INH will be observed during hospitalization, and adherence will be documented by study staff using hospital records.

6.0 CLINICAL AND LABORATORY EVALUATIONS

6.1 Schedule of Events

6.1.1 **Table 6.1-1:** Step 1

Evaluation	Screening	Step 1 Day 0 ²
Spot Sputum Collection	X	X ³
AFB Microscopy	X	
Genotypic DST with HAIN MTBDRplus	X	
Culture and Phenotypic DST Determination with MIC		X
Hospitalization ¹	X	

¹At the discretion of the investigator, some participants may be hospitalized during the screening evaluations, but this is not a requirement.

²The screening and Step 1 Day 0 visits may be combined for these participants.

³Step 1 Day 0 spot sputum collection is only required if the screening spot sputum is insufficient or inadequate for Step 1 entry evaluations.

6.1.2 Table 6.1-2: Step 2

Evaluation	Screening	Pre-entry	Entry: Registration/ Randomization	Study Treatment (Days)							Discharge	Final Visit	Premature Discontin- uation	
				Step 2 Day 0	1	2	3	4	5	6	7			
NAT2 genotype (blood and saliva)			X											
Chest X-ray	X ²													
Spot Sputum Collection			X ³											
Genotypic DST (MTBDRs) ⁴			X											
Overnight Sputum Collection		X	X	X	X	X	X	X	X	X	X			
EBA Analysis by Solid Culture CFU (Groups 1 and 2 only) Determination and Liquid MGIT Culture for TTD ⁵ (all groups)		X	X	X	X	X	X	X	X	X	X			
Pharmacokinetic Sampling										X				
Hospitalization	X ⁶	X	X	X	X	X	X	X	X	X	X			

¹Participants must have a negative serum or urine pregnancy test within 7 days prior to entry.

²A chest x-ray is not required at screening if results of a chest x-ray performed within 14 days prior to screening are available.

³Sputum from Step 1 (Screening or Day 0) may be used if there is an adequate amount for genotypic DST.

⁴For those participants who have MDR-TB identified by MTBDRplus.

⁵X's here refer to the date that the overnight sputum collection was begun. Assay will be conducted the next morning.

⁶At the discretion of the investigator, some participants may be hospitalized during the screening evaluations, but this is not a requirement.

6.2 Timing of Evaluations

6.2.1 Screening and Pre-Entry Evaluations

Screening

Screening procedures will be performed within the 2 weeks prior to entry unless otherwise noted to minimize participants' waiting time for a decision about whether or not they can be enrolled. In addition to data being collected on participants who enroll into the study, demographic, clinical, and laboratory data on screening failures will be captured in a Screening Failure Results form and entered into the ACTG database.

To avoid unnecessary delay in initiating TB treatment, screening evaluations for Step 1 and Step 2 may occur on the same day.

Recruitment will occur through the study site(s) and may include referrals of TB participants from outlying TB clinics and local or regional mycobacteriology laboratories. Participants with a presumptive diagnosis of sputum smear positive or GeneXpert-positive pulmonary TB will be invited to screen for the study.

NOTE: Some participants may be hospitalized during the screening period, at the discretion of the investigator, for the safety of the participant or to decrease risk of transmission to others.

Pre-entry

Only those participants who are expected to be enrolled in a treatment group will have this visit. At least 48 hours prior to the first dose of study medication, participants who will be enrolled in a treatment group will be admitted to the inpatient EBA unit at the study site to complete the pre-entry requirements. Two days prior to scheduled drug dosing, beginning at around 4pm \pm 1 hour, a 16-hour quantitative sputum collection will be performed. Participants who do not produce an overnight sputum sample of sufficient quality and quantity will be considered screen failures. However, if a participant's failure to produce sufficient sputum appears to be due to poor technique rather than low volume of sputum production, this evaluation may be repeated.

6.2.2 Entry Evaluations (Day 0)

6.2.2.1 Step 1, Day 0

Those participants registered to the study but not enrolled in a treatment group (i.e., Stages 1 or 2, Group 1 who do not meet Step 2 entry criteria; Stage 1, Groups 2 and 3; or Stage 2, Group 2 **or** 3 who do not meet Step 2 entry **criteria**) **will** only have sputum for phenotypic DST determination with MIC at this visit. This evaluation may be performed on sputum collected at Step 1 Day 0 or sputum collected at screening. Thus, the screening and Step 1 Day 0 visits may be combined for these

participants. After this evaluation is performed, the participant will be discontinued from the study.

6.2.2.2 Step 2, Day 0

Those participants enrolled in a treatment group will remain in the hospital until Day 8. Registration/randomization will occur on the day of study entry. A 16-hour quantitative sputum collection will be performed. Participants who do not produce an overnight sputum sample of sufficient quality and quantity on Step 2 Day 0 will be discontinued from the study (see [section 8.1](#)). However, if a participant's failure to produce sufficient sputum appears to be due to poor technique rather than low volume of sputum production, this evaluation may be repeated.

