6.2.3 Post-Entry Evaluations (for participants who meet Step 2 entry criteria)

Days 1-7 (Treatment)

Participants must begin treatment within 24 hours after registration/randomization. Participants will receive their assigned dose of INH in the morning on an empty stomach, defined as nothing by mouth except water and study medications 2 hours pre-dose and 1 hour post-dose.

Day 8 (Discharge)

Those participants enrolled in a treatment group will be discharged from the hospital on Day 8. Upon discharge from the hospital and no later than Day 10, participants will be referred to the standard local TB treatment.

Final Visit

This visit will occur 14 (± 3) days after the final dose of study medications to evaluate for evidence of delayed toxicity and to follow up on any adverse events (AEs) that occurred during the study.

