6.3.9 Sputum Samples

Spot Sputum Collection

Spot sputum will be collected for the following:

Genotypic DST (MTBDRs)

Among those participants with MDR-TB, Hain MTBDRs/ testing for detection of fluoroquinolone **and injectable TB drug resistance** will be performed.

Overnight Sputum Collection

Sputum will be collected over 16 hours each night beginning at around 4pm ±1 hour, and each participant's overnight sputum samples will be pooled in an appropriate, clean container. This sputum will be used for the following:

EBA Analysis by Solid Culture CFU Determination and Liquid MGIT Culture for TTD

Sputum will be cultured on solid media, and CFU count will be determined **for Groups 1 and 2 only. For all groups** daily TTD determination will be done, and measured in hours.

Start and stop times, total volume collected, and any interruptions in collection or temperature control problems will be recorded.

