8.0 CRITERIA FOR DISCONTINUATION

8.1 Premature Study Discontinuation

- Inability to produce an overnight sputum sample of sufficient quality and quantity over a 16-hour collection period on Step 2 Day 0
- Grade ≥ 3 drug-related AE or toxicity or any Grade 4 AE or toxicity (see [section 7.1](#) Toxicity)
- Requirement for prohibited concomitant medications (see [section 5.4](#))
- Failure by the participant to comply with inpatient hospital stay
- Pregnancy

- Nonadherence with one or more doses of study treatment
- Development of another medical condition that makes the administration of one or more planned doses of study drug inadvisable
- Inability to provide a study-required sputum sample at any time through day 8
- Request by the participant to stop study treatment or withdraw
- It is the investigator's judgment that it is no longer in the best interest of the participant to continue study participation.
- At the discretion of the ACTG, IRB/EC, NIAID, Office for Human Research Protections (OHRP), or other government agencies as part of their duties, or the investigator.

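### The repeat allowed for a failed Day 0 sputum collection cannot be drug-free within 24 hours of a Day 0 randomization, and the sample is judged only after the dose is assigned

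*Protocol*

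**What the plan says.** Protocol 6.2.2.2 covers Step 2 Day 0. It places randomization and the second drug-free sputum collection on the same day: "Registration/randomization will occur on the day of study entry. A 16-hour quantitative sputum collection will be performed". A participant whose Day 0 sample is inadequate is discontinued, but if the failure appears to be due to "poor technique rather than low volume of sputum production, this evaluation may be repeated".

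The sections that bear on this are:

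- Protocol 6.2.3: "Participants must begin treatment within 24 hours after registration/randomization", and "Participants will receive their assigned dose of INH in the morning on an empty stomach". Section 5.1 puts the doses on Days 1-7.
- Protocol 6.3.9: "Sputum will be collected over 16 hours each night beginning at around 4pm ±1 hour". Footnote 5 of the schedule in 6.1.2 labels each collection by the date on which it starts, and a collection is scheduled for every treatment day, including Day 1.
- Protocol 8.1 lists as a reason for premature discontinuation: "Inability to produce an overnight sputum sample of sufficient quality and quantity over a 16-hour collection period on Step 2 Day 0". Section 9.4 replaces participants who discontinue before the Day 7 evaluations.
- Protocol 9.2.1 and SAP 3.2 define baseline as the mean of the pre-entry and Day 0 values, for both CFU and TTD.
- Protocol 6.2.1 treats an inadequate pre-entry sample, collected one night earlier and before randomization, as a screen failure, also with a repeat allowed.

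**The concern.** Two things do not fit.

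The first is timing. The repeat is permitted, but no section says how it affects the 24-hour limit, the Day 1 dose, the day numbering or the choice of entry specimen. A site that uses it must either delay the first dose past the limit or collect the repeat after dosing has begun. In the second case the same night's sputum is also the scheduled Day 1 sample. The Day 0 value is half of the baseline in both EBA0-7 endpoints. An on-drug value in that place lowers baseline log10 CFU, or lengthens baseline TTD, and pulls EBA0-7 toward zero, most where the drug is most active.

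The second is the order of steps. The adequacy of the Day 0 sample is decided after an open-label assignment. Whether a failure is technique (repeat allowed) or low volume (out and replaced) is a judgement that can be made with the dose known. The threshold for adequacy is itself unclear: Protocol 4.3.9 gives a guideline of 10 mL, while the note in SAP 4.2 uses 1 mL. A randomized participant lost at this point has taken no dose and so leaves both the safety and the primary efficacy populations in SAP 3.1.

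**Working it through.** **Inputs.** Randomization on Day 0, hour not stated (6.2.2.2). Limit of 24 h to first dose (6.2.3). Morning dosing, first dose on Day 1 (5.1, 6.2.3). Collections of 16 h starting 15:00-17:00 (6.3.9). For size: planning means of 0.105 (Group 1) and 0.21 (Group 2) log10 CFU/mL/day, SD 0.12 and n = 16 (9.4); 90-95% kill of susceptible strains in two days (2.1).

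**Step 1: the schedule without a repeat.** The Day 0 collection ends at 15:00-17:00 plus 16 h, which is 07:00-09:00 on Day 1. A dose straight after it meets the limit provided that randomization was no more than 24 h before the dose. Randomization at 16:00, for example, gives a gap of 15-17 h. The 24-hour figure is workable here.

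**Step 2: the schedule with one repeat.** The repeat starts at 15:00-17:00 on Day 1 and ends at 07:00-09:00 on Day 2.

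| Randomized on Day 0 at | Hours to end of first collection | Hours to end of repeat | Over the 24 h limit by |
|---|---|---|---|
| 08:00 | 23-25 | 47-49 | 23-25 |
| 12:00 | 19-21 | 43-45 | 19-21 |
| 16:00 | 15-17 | 39-41 | 15-17 |
| 23:59 | 7-9 | 31-33 | 7-9 |

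No Day 0 hour works. Day 2 begins 24 h after Day 0 ends, so any Day 2 dose is late. For the repeat to fit, randomization would have to be at 07:00-09:00 on Day 1 or later. Restarting straight after the failed collection does not help: it would depart from the stated start time, run until 23:00-01:00, and still leave the next morning dose on Day 2.

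**Step 3: the limit kept, first dose on Day 1.** With a dose at 08:00-09:00 (assumed), the repeat begins 6-9 h after dosing, on the night of the scheduled Day 1 sample.

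**Step 4: size, if that specimen were used as the entry value.** EBA0-7 = [(pre-entry + Day 0)/2 − Day 7]/7. If the Day 0 value is lower by d, baseline falls by d/2 and EBA0-7 by d/14. Take d as one full day of effect (assumption).

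- Linear decline: d equals the daily rate, so the loss is 1/14 = 7.1%. That is 0.105/14 = 0.0075 in Group 1 and 0.21/14 = 0.015 in Group 2. The same 1/14 applies to the magnitude of EBA0-7(TTD) if TTD changes linearly.
- Front-loaded kill in susceptible strains: −log10(0.10) = 1.00 and −log10(0.05) = 1.30 over two days, or 0.50-0.65 per day. Divided by 14 this is 0.036-0.046, and 0.036/0.21 to 0.046/0.21 is 17-22%.

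**Step 5: effect on a cohort.** One case in 16 moves the mean by 0.036/16 to 0.046/16 = 0.0022-0.0029. The planned half-width reproduces: 2.131 × 0.12/√16 = 0.0639, stated as 0.064. The shift is under 5% of it (0.0029/0.064 = 4.5%).

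**The case against.** The other side has a good deal to say.

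- The repeat is optional. Without it the schedule fits the 24-hour limit, and the default for a failed sample is to discontinue and replace. A reader might infer that baseline is routinely taken on drug or the limit routinely broken; the documents do not support that.
- No section says that a post-dose specimen becomes the entry value. The labelling footnote would make it the Day 1 sample. SAP 3.1 restricts the primary analysis to participants with entry and Day 7 data, and SAP 4.1 points to the model-based analysis when such values are missing. So an on-drug baseline is a possibility left open, not something the plan directs.
- A reader might call this an eligibility test applied after randomization. Formally it is not: criterion 4.3.9 is tested at the pre-entry collection, before randomization, and the Day 0 rule is a discontinuation rule. It does, however, re-apply the same standard of sample adequacy once the dose has been assigned.
- A reader might infer that the randomized dose comparison is undermined. The analyses are descriptive, cohort by cohort (Protocol 9.6.1, SAP 4.3.1). Group 2 takes a single dose and is not randomized, and the Group 3 dose effect is to be examined visually.
- The 17-22% divides a two-day kill rate by a five-day mean, applies only to susceptible strains, and credits a full day's kill to a sample begun hours after the first dose. It is an upper illustration.
- Section 8.1 does not mention the repeat, but 6.2.2.2 states it next to its cross-reference to 8.1, so that omission is minor.

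These points limit how often the problem arises and how large it is. They do not remove the conflict: whenever the repeat is used, 6.2.2.2, 6.2.3 and 6.3.9 cannot all be followed with a drug-free sample.

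**Conclusion.** The point holds in conditional form. A Day 0 repeat at the stated start time ends 31 h or more after any Day 0 randomization, at least 7 h past the limit, and this does not depend on the unstated hour of randomization. When the repeat is not used, a randomized participant can be dropped and replaced on a judgement that may be made with the dose known.

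The likely numerical effect is small. For one participant whose post-dose repeat served as the entry value, EBA0-7 would lose about 7% under linear decline and at most 17-22% in susceptible strains. One such case moves a 16-person mean by at most about 0.003 log10 CFU/mL/day. These sizes assume one full day of drug effect in the repeat and an unaffected pre-entry value. The documents do not say how often repeats occur, so the total effect cannot be given. The case for acting is that the rules conflict on a component of the primary endpoint and the correction is cheap.

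**What to change.** 1. In Protocol 6.2.2.2, 4.5.2 and the schedule in 6.1.2, complete registration/randomization after the Day 0 overnight sample, or its repeat, has been accepted and before the first dose. Sample adequacy is then judged before the dose is known, and the wording of the 24-hour limit need not change.
2. In SAP 3.2, state that a repeated Day 0 specimen begun after dose 1 does not enter the baseline mean, and say whether the pre-entry value alone then serves as baseline or the participant is handled only in the model-based analysis.
3. Reconcile 6.2.2.2, 6.2.3, 6.3.9 and 8.1 on how a repeat affects the 24-hour limit, day numbering and discontinuation. The content of the discontinuation rule is for the sponsor to settle.

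Cost: amendment wording, with assignment and tablet preparation on the morning of dosing. When a repeat is used, there is one more inpatient night and a start one day later. For Groups 1 and 2, whose report is dated September 2018 (SAP 5), only the check for post-dose specimens in the baseline is relevant; the same holds for anyone already enrolled in Group 3.
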